9.4 Use of core outcome sets

There is a newly developed core outcome set for gastric cancer surgery [21], however this has not been validated as yet and is not applicable to this surveillance study. We have thus included common core outcomes where applicable.

10 STUDY DESIGN AND SETTING

The SARONG study is a multi-centre, open-label, two-arm, parallel design, superiority randomised controlled trial. 952 patients (476 in each of two trial arms) will be recruited from approximately 24 sites in the UK. Participants will be randomised to either intensive surveillance (including radiological scans) every 6 months for 36 months and an endoscopy at 12 months post-randomisation or standard care follow-up for 36 months.

A study flow chart is provided in APPENDIX 1 – STUDY FLOW CHART.

10.1 Recruiting sites/site types

Participants will be recruited from approximately 24 NHS oesophago-gastric centres across the United Kingdom.

10.2 Collection of outcome data and follow-up assessments

All clinical follow-up visits will either be face-to-face appointments or by telephone consultation in accordance with local site practice and the participant's randomised allocation. Participants will be sent all HRQoL questionnaires and healthcare resource use questionnaires via email with a link to complete questionnaires online, with an option to complete the questionnaires via telephone call from the Surgical Intervention Trials Unit (SITU) post if the patient expresses this as a preference. HRQoL questionnaires will be administered in English. Non-native English speakers will be permitted to use support to complete the questionnaires as needed.

Clinical outcomes and resource usage in secondary care will be collected by local study teams and recorded in the case report form in the REDCap database. Refer to section STUDY ASSESSMENTS/PROCEDURES for details of the data being collected in the study and the timepoints and methods for this data collection.

Participating study centres will describe the indication for further investigations and if this met the defined symptomatic threshold (see section 14.2.1 Definition of alarm symptoms) or was a protocol deviation.

Data on all-cause 3-year mortality will be collected from the participant's medical record and validated against National Oesophago-Gastric Cancer Audit (NOGCA) [22] and Office of National Statistics (ONS). The process of validation will begin after 12-months of recruitment and then continue every 6 months during the study. Data regarding timing, centre and treatment of recurrence, and 3-year disease specific mortality will be recorded on the CRF by the local centre study team using the participant's medical record. Specific approval has been gained from the audit to support the SARONG study and integration of this data within the national audit processes. Data on treatment of recurrence will be collected from the participating centres on the CRF.

Any discrepancies identified between centre-reported data collected on the case report form and data derived from the registries will be discussed with the participating site to verify the correct data. Data discrepancies will be handled in accordance with the study-specific data management and monitoring plan.

Refer to section17 STUDY ASSESSMENTS/PROCEDURES for full details of outcome data collection and follow-up assessments.

10.3 Duration of participant involvement

Participants will be in the study for approximately 36 months from randomisation to last protocol visit. Mortality and recurrence data will be collected for 36 months after the last participant is randomised, this data will be collected from medical records and in the case of all-cause mortality validated against NOCGA and NCRAS.

10.4 Post-study treatment/care and follow-up

Following a participant's final protocol visit, they will receive standard care from their participating institution.

10.5 Central review procedures

10.5.1 Quality assurance of radiology reporting

During the internal pilot phase (see Internal pilot/Decision Points), all CT scans from participating centres will be sent by the local centre team to a central repository housed within the secure Oxford University Hospitals NHS Foundation Trust's Secure Data Environment server (OUH NHSFT SDE). Images will be sent for participants in both arms of the study; any CT scans for images taken as part of standard care in the standard care arm will be requested. All images will be identifiable only by the participant's Study ID. These will be transferred securely by e-mail from a nhs.net e-mail address. If the files are unable to be transferred via email, another secure service, approved by the affected site, and compliant with the relevant OCTRU SOP will be used. Images will be re-reviewed by a senior Oxford consultant radiologist, with discrepancies discussed with the local radiology reporting lead at the participating site to ensure standard (internal audit) during this internal pilot phase.

Following the internal pilot phase, each site will be requested to send a randomly selected 10% of all CT images every 6 months to the secure OUH NHSFT SDE server. The radiological lead at Oxford will direct the quality assurance program to validate these reported radiological images, with any discrepancies discussed with the local radiology reporting team. Images will be either reported as positive, indeterminant or negative for recurrence. Within the positive recurrence group, oligometastatic recurrence will be characterised and classified according to current European recommendations [23]. Indeterminant lesions will be further investigated and characterised as per local participating centre protocols.

10.6 Use of NHS England data (including data from registries)

The NOGCA is commissioned by the Healthcare Quality Improvement Partnership (HQIP) as part of the National Clinical Audit and Patient Outcomes Programme (NCAPOP). The data processes and validation of the entered data has been well established for patients receiving surgery for oesophageal and gastric cancer since 2012. This national audit is used by all oesophago-gastric specialist cancer centres in England and Wales for the entry of oesophageal and gastric cancer patients undergoing treatment both curative and palliative.

Participants from the SARONG study will be consented for linkage of their data to the Office of National Statistics (ONS) and NOGCA datasets. Locally collected data from participant medical records will be checked against mortality data from ONS, and from NOGCA.

Patients that decline to take part in the study will continue to have their data collected as part of their normal clinical surveillance and recorded within NOGCA. Data will also be collected regarding

additional radiological and endoscopic imaging during surveillance, to evaluate if a change in surveillance protocols has been observed within participating centres during the study, in non-study participants. Thus, the external validity of the study findings will be tested through comparison of the SARONG study data, with NOGCA data from non-participating patients and centres.

10.7 Health Economics

A cost-utility analysis to assess the cost-effectiveness of implementing an intensive surveillance after oncological treatment compared with current practice will be conducted.

Participants will be asked to complete a resource use questionnaire which will collect healthcare (primary care appointments, prescribed and over the counter medications, hospital admissions outside of their participating institution, contact with other healthcare professionals) and non-healthcare resource use (social and informal care, travel costs and time off work) of participants in both arms of study. The questionnaires will be administered to patients at baseline and at 6, 12, 18, 24, 30 and 36-months post-randomisation. Secondary care resource usage at the participating institution will also be collected from the participant's medical records.

The EQ-5D-5L instrument will be used to measure HRQoL at baseline and at 6, 12, 18, 24, 30 and 36-months post-randomisation.

Refer to section 20.12 for full details of the health economic analysis.

10.8 Expected recruitment rate

Each of the 24 oesophago-gastric centres planned to take part in the SARONG study currently undertake 50 to 150 oesophageal or gastric resections per year. It has been conservatively estimated that 35% of eligible patients will consent to take part in the study. We estimate that we will open at least 1-2 sites per month starting in June 2023 and that all sites will be open to recruitment within 15 months. Therefore, we are expecting 32 months of recruitment across 24 NHS sites. The expected recruitment rate for this study is 2-3 patients per month / per site based on a staggered opening of sites and assuming a recruitment of 35% of eligible participants.

11 TRANSLATIONAL STUDY/MECHANISTIC STUDY

Machine learning on computerised tomography images for detection of tumour recurrence

Anonymised CT images will be used to create a repository of CT scans, which will be used to test the accuracy of a recurrence identification model [15].

12 PARTICIPANT ELIGIBILITY CRITERIA

Participant eligibility will be confirmed by a suitably qualified and experienced individual who has been delegated to do so by the Principal Investigator.

12.1 Timing of eligibility assessment

Eligibility will be assessed upon initial entry into the study and checked at the point of randomisation.

12.2 Overall description of trial participants

The SARONG study will recruit adults aged 16 years and over who have undergone surgical resection for curatively intended oesophageal and gastric cancer with or without neoadjuvant/adjuvant chemotherapy or radiotherapy or immunotherapy (or in combination).

Written informed consent must be obtained before any study specific procedures are performed.

The Investigator (or designee) will determine patient eligibility based on the following criteria.

12.3 Inclusion Criteria

A patient will be eligible for inclusion in this study if all of the following criteria apply:

- 1. Has undergone surgical resection for curatively intended treatment of oesophageal or gastric cancer (adenocarcinoma and squamous cell carcinoma) with or without neoadjuvant/adjuvant chemotherapy or radiotherapy or immunotherapy (or in combination).
- 2. Aged 16 years or over
- 3. Willing and able to give informed consent

12.4 Exclusion Criteria

A patient with not be eligible for the trial if **ANY** of the following apply:

1. Has other cancers undergoing treatment or surveillance for this cancer

12.5 Rationale for inclusion and exclusion criteria

The vast majority of patients in the UK with oesophageal or gastric cancer are over the age of 16 years. Those under 16 years of age, will typically have a specific genetic mutation (for example CDH1), which is often associated with other cancers requiring treatment and formal surveillance. Patients undergoing treatment or surveillance for another cancer will be excluded from inclusion.

12.6 Protocol waivers to entry criteria

Protocol adherence is a fundamental part of the conduct of a research study. There will be no waivers regarding eligibility i.e. each participant must satisfy all the eligibility criteria. Changes to the approved inclusion and exclusion may only be made by a substantial amendment to the protocol.

Before entering a patient into the study, the Principal Investigator or designee will confirm eligibility. If unsure whether the patient satisfies all the entry criteria and to clarify matters of clinical discretion investigators must contact the study office, who will contact the Chief Investigator or designated clinicians as necessary. If in any doubt the Chief Investigator must be consulted before entering the patient. Details of the query and outcome of the decision must be documented in the TMF/ISF.

12.7 Clinical queries and protocol clarifications

Every care has been taken in drafting this protocol. Contact the Study Office for clarification if any instructions seem ambiguous, contradictory or impractical. Clinical queries must also be directed to the Study Office. All clinical queries and clarification requests will be logged, assessed and a written response provided. Minor administrative corrections or clarifications will be communicated to all trial investigators for information as necessary. For urgent safety measures or changes that require protocol amendment see section 24.8.

12.8 Compliance with NIHR INCLUDE guidance

Data provided by CRUK describe that the incidence rate for oesophageal and gastric cancer is highest in people over 75-years-old, every year 4 in 10 (41%) of all new oesophageal cancer cases and each year half (50%) of all new stomach cancer in the UK are diagnosed in people aged 75 years and over (2016-2018). The prevalence of both cancers is higher in deprived areas in both genders. Stomach

cancer incidence rates for persons are lower in the Asian ethnic group, higher in the Black ethnic group, and similar in people of mixed or multiple ethnicity, compared with the White ethnic group, in England. Incidence rates for oesophageal cancer are lower in the Asian and Black ethnic groups, compared with the White ethnic group, in England (2013-2017) [24]. Therefore, we believe that the under-served groups for this study are associated with two main demographics factors; age extremes and different ethnic minority groups and social and economic factors such as patients living in deprived areas.

The study includes anyone who has been treated with surgery for both these cancers and is eligible to take part of the study. We do not foresee any differences between our study population and the broader population with oesophageal and gastric cancer undergoing surgery.

We will promote a patient-oriented retention method where participants can choose their preferred method of communication for follow up questionnaires. During the first post-operative visit (baseline) with the local study team, if the patient decides to take part in the study, we will ensure that participants can decide how to receive their questionnaires over the three years of the study (for example, electronically, by telephone or by mail).

This will allow us to accommodate the needs of the elderly, populations with limited access to technology, or other vulnerable populations, with the provision of postal or telephone follow up. The use of electronic questionnaire follow ups will also allow convenience for many participants, and the ability to use any other accessible technologies they may use in daily life (e.g. screen readers, increased font size).

13 SCREENING AND RECRUITMENT

13.1 Participant Identification

Participants will be recruited from oesophago-gastric centres and referring hospitals within the NHS in the United Kingdom

The following methods will be used to identify potentially eligible participants:

- Identification during routine clinical or ward visits.
- Searching of clinic records/hospital database by the usual care team to identify individuals that may be eligible

A poster advertising the study may be displayed in electronic and paper formats as allowed in participating centre. All advertising material will be approved prior to use.

13.1.1 Identification of participants during routine clinical visits

Potentially eligible patients identified during routine clinic visits will be provided with a Patient Information Sheet (PIS) by a member of their usual care team (who may also be a member of the study team) and asked to consider the study. Where their usual care clinician is not a member of the local study team potential participants will be asked if it would be acceptable for their name to be passed to the local study team to make contact (this may be in person in clinic or via telephone or video call), or potential participants may be given the PIS and asked to call the number on it if they wish to find out more about the study. When a potential participant is approached for permission for their details to be passed onto the local study team – if this permission is given this should be recorded in their clinical notes.

The initial approach about this study will usually take place after surgery. Patients will be consented for inclusion in the study and eligibility confirmed at least 24 hours after the initial approach and within approximately 12 weeks of their surgery. Randomisation will take place after the baseline data are collected. Consent will be taken in clinic electronically, or obtained using remote eConsent.

13.1.2 Identification of participants via clinic records/hospital database

Potentially eligible participants will be identified by searching of clinic records/hospital databases by those in the clinical care team only. Any patients who are thought to fulfil the inclusion/exclusion criteria will be approached about the study after surgery within approximately 12 weeks.

13.2 Use of screening logs

A screening log must be kept of all patients considered for the study including any that are subsequently excluded; the reason for exclusion must be recorded on this form.

Screening logs will be used to record information about the number of patients considered and/or approached for the study and if provided, the reasons for declining participation.

13.3 Use of social media

Twitter/X feeds may be utilised to promote the study, and acknowledge when milestones are met (e.g. sites open to recruitment, first recruitment at a site etc).

14 STUDY INTERVENTION AND COMPARATOR

14.1 Intensive surveillance follow-up (intervention)

Participants randomised to the intervention arm will receive intensive surveillance for three years. Participants will have a clinical review with a CT scan of the chest, abdomen and pelvis every 6 months up to 36 months. An endoscopy will also be performed 12 months post-randomisation.

14.2 Usual care (comparator/control)

Participants randomised to the comparator arm will receive standard care follow-up following their surgery. Standard care comprises of a clinical review at 6 and 12 months and after 12 months, participants are either discharged to primary care or clinically reviewed annually by the treating centre, with targeted investigations as needed. Targeted investigations are recommended in the event of new onset alarm symptoms (see section 14.2.1 below).

14.2.1 Definition of alarm symptoms

Participants randomised to the control arm will undergo further endoscopic or radiological investigation for cancer recurrence at the discretion of local centre if they experience any of the following symptoms:

- dysphagia to solid food
- dysphagia to liquids
- vomiting
- abdominal pain
- chest pain
- regurgitation of foods
- unexpected weight loss
- progressive hoarseness of voice

Investigations triggered by the presence of these symptoms, along-with deviations from this assigned pathway, will be collected on the CRF and for participants in both study arms during the follow-up period. Significant deviations from the established symptomatic threshold, defined as more than 10% of patients in the control arm from centre in a 6-month period, will trigger feedback and monitoring of the participating centre.

15 INFORMED CONSENT

15.1 Consent Procedure

Informed consent will be sought and if a person approached is willing to give consent it will be obtained by a member of the study team listed on the delegation log before they undergo any interventions/assessments related to the study. A member of the local study team will explain the details of the study in addition to the already presented PIS, ensuring that the potential participant has sufficient time to consider participating or not. A member of the local study team (authorised to do so on the delegation log) will answer any questions that the potential participant has concerning study participation.

The Investigator who obtains consent must be suitably qualified and experienced. All delegates must be authorised by the site Principal Investigator to obtain consent. The Investigator is responsible for ensuring that the study consent procedures comply with current applicable GCP Regulatory and ethical requirements. Informed consent discussions and outcomes must be well documented in the medical record. The Investigator must be satisfied that the patient has made an informed decision before taking consent.

15.2 Completion of the Informed Consent Form (ICF)

The Informed Consent Form will usually be offered to participants in clinic as an electronic form on a tablet device (with the consent form being filled in directly on the study database, REDCap.) Where it is not possible for a consent form to be completed in clinic (for example, if a participant has only had telephone appointments), remote electronic consent may be used.

A copy of the fully signed ICF will be given to the participant; where electronic consent is used and the participant has an email address they are willing to provide, an electronic version of the signed ICF will be automatically emailed to them. If the participant does not have/does not provide an email address the local study team will be able to print a copy of the signed ICF and provide this to the participant. Consent forms will be e-mailed securely to the participant. The electronic signed consent form will be held securely in the study database. A copy will be downloaded from the study database and should be placed in the participant's medical record.

Remote eConsent (using REDCap) will be obtained in accordance with OCTRU's standard operating procedures for obtaining consent. Where remote consent will be used, potential participants will be asked to provide an e-mail address for receiving consent documents prior to obtaining written informed consent. Potential participants will receive a unique link via e-mail to an electronic consent form which may then be completed remotely, once completed this form will be sent, via e-mail, to the participant as a PDF document. A member of the local study team will be required to countersign all consent forms completed remotely, in the same way as for paper forms and verify the identity of the participant. Participants that do consent to study participation will receive a copy of the fully completed consent form via e-mail once this has been countersigned.

15.3 GP notification

Participants will be made aware as part of the informed consent process that if they consent to take part in the study their GP will be informed of their participation in the study. Explicit consent will be obtained from the participant for this and an approved GP letter will be sent by the local centre to the participant's GP informing them of their participation in the study together with study information.

15.4 Re-consenting

Should there be any subsequent amendment to the final protocol, which might affect a participant's participation in the study, continuing consent will be obtained using an amended consent form which will be signed by the participant.

15.5 Participants who lose capacity during the study

Participants that lose capacity during the study will be withdrawn from the study.

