17.3 Withdrawal of Participants

17.3.1 Withdrawal of consent by the participant

Withdrawal of consent means that a participant has expressed a wish to withdraw from the study altogether, or from certain aspects of the study only. The type of withdrawal will be collected on the Withdrawal CRF.

Participants may also be withdrawn from the study (or aspects of the study) by their clinician if they believe the participant needs to be withdrawn.

The Withdrawal CRF should be completed to document the reasons for withdrawal, and state who made the decision to withdraw. Discussions and decisions regarding withdrawal should be documented in the participant's medical notes. Investigators should continue to follow-up any SAEs and should continue to report any SAEs to resolution in the CRF in accordance with the safety reporting section.

Where a participant expresses a wish to withdraw from the study, the study team will determine which aspect(s) of the study the participant wishes to withdraw from; all other aspects of the study/follow-up will be continued. The local study team should discuss with the patient if they accept subsequent data (including routine care data) to be collected as part of the study. This data as a minimum would be data from medical records, ONS and NOGCA for the analysis of mortality as the primary outcome of the trial.

The aspects of the study that the participant may request to withdraw from are as follows:

- No longer willing to receive study intervention
 - participants would have no more CT scans than standard of care, but would continue active follow-up to complete the study questionnaires and allow continued collection of data from medical records that is recorded as part of routine standard care).
- No longer willing to complete study questionnaires
 - this refers to the health-related quality of life questionnaires and Healthcare Resource
 Use questionnaires sent directly to participants by the study office
- No longer willing to have standard of care data from the medical record provided to the study
- No longer willing for standard of care data from Health data providers e.g. NHS digital, to be provided to the study
 - o this refers to data from ONS and NOGCA

Data collected up to the point of withdrawal will be used in the study analysis, or beyond depending on the specific type of withdrawal described above.

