20.4 Description of Statistical Methods

Results will be reported in line with the CONSORT statement.

All analyses will be carried out on the intention-to-treat population (i.e. all patients will be analysed in the group that they were randomised to regardless of the actual treatment received). It is not anticipated there will be any protocol deviations, however, in the event that any occur, we will

repeat the primary analysis for the per protocol population (patients excluded from the per-protocol population will be pre-specified in the SAP).

Standard descriptive statistics will be used to describe the demographics between the two follow-up regimens; reporting means and standard deviations or medians and inter-quartiles ranges as appropriate for continuous variables and numbers and percentages for binary and categorical variables. All comparative outcomes will be presented as summary statistics and reported together with 95% confidence intervals. All tests will be carried out at a 5% significance level.

It is anticipated that all statistical analysis will be undertaken using Stata (StataCorp LP, www.stata.com) or other well validated statistical software.

Primary outcome

The primary outcome is overall survival. An event is defined as death from any cause. Participants who have not died during the trial will have their survival time censored at their last known alive date. This includes participants who withdraw from the trial.

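### Withdrawal on loss of capacity (15.5) has no provision for continued death ascertainment, which opens a route to prognosis-related censoring of the all-cause mortality endpoint

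*Protocol*

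**What the plan says.** Section 15.5 is a single unqualified sentence: "Participants that lose capacity during the study will be withdrawn from the study". It has no option to withdraw from part of the study and no exception for mortality data.

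Section 17.3.1 handles withdrawal in more detail. Its aspect-by-aspect process is triggered when a participant expresses a wish to withdraw. The local team is then to ask the patient whether further data may be collected, and the text adds: "This data as a minimum would be data from medical records, ONS and NOGCA for the analysis of mortality". Data from after withdrawal are used according to which of the listed types applies. Those types are study intervention, questionnaires, medical-record data and registry data. The same section says: "Participants may also be withdrawn from the study (or aspects of the study) by their clinician if they believe the participant needs to be withdrawn".

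Section 20.4 defines the event as death from any cause and censors those who have not died at the date last known alive, adding: "This includes participants who withdraw from the trial". Section 20.10 concludes from this censoring rule that the primary outcome cannot have missing data.

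Three other places bear on the point. Section 10.3 promises mortality and recurrence data for 36 months after the last randomisation, without exception. Section 10.6 says participants consent to linkage with ONS and NOGCA. Section 19 takes a participant who becomes pregnant off the intervention but expressly provides for continued collection from medical records.

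**The concern.** The safeguard in 17.3.1 depends on a wish expressed by the participant and a conversation with them. A person who has lost capacity cannot supply either, and loss of capacity is not a listed withdrawal type. The default reading is therefore that data are used up to withdrawal and then stop.

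In this population, loss of capacity plausibly clusters towards the end of life. That is a clinical inference which the documents do not quantify. If it is right, censoring at that point is informative, whereas the Cox and log-rank analyses assume it is not. Observed mortality would be understated in both arms.

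The hazard ratio would be biased if the loss differed by arm. The trial is open label, and section 17.1 schedules six post-randomisation reviews in the intervention arm against two in control, so loss of capacity could be noticed and acted on at different times. Disease-specific mortality and recurrence (section 9.3) would lose the same people. The statement in 20.10 would hide the problem, because a censored record looks complete.

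**Working it through.** **1. The passages side by side**

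| Reason for leaving | Section | Mortality follow-up afterwards |
|---|---|---|
| Participant's wish | 17.3.1 | Records, ONS and NOGCA as a minimum, if the patient accepts |
| Pregnancy | 19 | Collection from medical records expressly provided for |
| Clinician's decision | 17.3.1 | Whole or partial withdrawal; nothing said on mortality data |
| Loss of capacity | 15.5 | Whole study; nothing said on mortality data |

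**2. The plan's own figures (section 20.2)**

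- Hazard ratio = ln(0.55)/ln(0.45) = 0.5978/0.7985 = 0.7487, stated as 0.749.
- Deaths (Schoenfeld, 1:1) = 4(1.960 + 1.282)²/(ln 0.7487)² = 502, which matches 273 + 229.
- Sample size: exponential survival, uniform 3-year accrual, 3-year minimum follow-up and 10% loss **per year** give 502/0.528 = 950 participants, with 273.6 and 229.5 deaths at 476 per arm. The stated figures are 952, 273 and 229. The protocol does not say whether its 10% is annual or total; total loss spread over 3 years gives only about 840 to 851.

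The design figures reproduce and are not in dispute.

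**3. Equal loss in both arms (share x of deaths assumed)**

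If participants are censored shortly before death, the observed death hazard is roughly multiplied by (1 − x).

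- At x = 5%: 502 × 0.95 = 477 deaths.
- Power = Φ(0.2894 × √477/2 − 1.96) = Φ(1.20) = 0.885. With the rounded 0.749 it is 0.884.
- Apparent 3-year control mortality = 1 − exp(−0.7985 × 0.95) = 53.2%, against 55%.
- The hazard ratio is essentially unchanged, because both hazards scale alike.
- At x = 10%: 452 deaths, power 0.867, control mortality 51.3%.

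**4. Unequal loss (shares assumed)**

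The hazard ratio is multiplied by (1 − intervention share)/(1 − control share).

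| Control / intervention share lost | Multiplier | HR if truly 0.749 |
|---|---|---|
| 6% / 3% | 0.97/0.94 = 1.032 | 0.773 |
| 3% / 6% | 0.94/0.97 = 0.969 | 0.726 |
| 10% / 5% | 0.95/0.90 = 1.056 | 0.791 |
| 5% / 10% | 0.90/0.95 = 0.947 | 0.710 |

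For 10%/5%, 273 × 0.90 + 229 × 0.95 = 463 deaths and power is about 0.715. Under a true null, either 10-against-5 pattern gives a two-sided type I error of about 0.09 at those event counts. These last rows mark the upper end of the range and are not a forecast.

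**The case against.** The strongest reply is that the deaths would be found anyway. Section 20.4 censors only participants not known to have died, and at the last date known alive, not at withdrawal. Participants consent to ONS and NOGCA linkage while they have capacity (10.6). Mortality is checked against those sources every 6 months (10.2, 21.1), and NHS/CHI numbers are held for registry queries (24.13). All of this is correct, and it means that lost deaths are a consequence the wording permits, not one it states. It does not close the gap, because nothing says that linkage or record review continues after a 15.5 withdrawal, and a plain reading of withdrawal from the study is that it does not.

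A reader might infer more than the documents support, in two ways.

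- **Clinician withdrawal necessarily loses deaths.** It need not: the sentence allows withdrawal from aspects only, and the Withdrawal CRF records the type and who decided. Loss is possible there, not certain.
- **Section 20.5 is breached.** It is not: a censored participant is still included, in the allocated arm. The issue is bias from censoring, not exclusion from the intention-to-treat population.

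Two further limits stand. The consent form is not available here, so it may already cover continued follow-up. The power loss may also be partly double-counted, since the 502 deaths are already net of the plan's loss allowance. That allowance does not help with bias, because it treats loss as unrelated to prognosis.

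**Conclusion.** The point holds as a defect in a stated rule. Section 15.5 prescribes whole-study withdrawal, the 17.3.1 safeguard does not reach it, and the result sits badly with the follow-up promised in 10.3 and the claim in 20.10. The protocol writes the needed exception for pregnancy but not here.

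Its size is unknown. Every loss rate used above is assumed, as are the closeness of capacity loss to death and any difference between arms; the documents do not indicate which arm would lose more. Equal loss of around 5% would cost little power and leave the hazard ratio alone while understating absolute mortality by about 2 percentage points. The main risk is unequal loss: about 3% on the hazard ratio at 6% against 3%, in either direction. The case for acting rests on how cheaply an avoidable source of informative censoring on the primary endpoint can be removed, not on a demonstrated large effect.

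**What to change.** 1. **Section 15.5:** say that loss of capacity ends study procedures and questionnaires only. Vital status, cause of death and recurrence continue to be collected from medical records and ONS/NOGCA to the common cut-off of 36 months after the last randomisation, under the consent given at entry. This is subject to ethics approval and to checking that the consent wording covers it.
2. **Section 17.3.1:** state that the same minimum mortality data are kept after clinician-initiated withdrawal unless the participant declines, and add loss of capacity to the withdrawal types for which later data are used.
3. **Section 20.10:** replace the statement that no primary outcome data will be missing with one that recognises early censoring as incomplete follow-up.

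The cost is a protocol amendment with ethics review, plus a consent-form change only if the check shows one is needed. There are no extra visits, no new data source and no change to the sample size. It is best done early, because deaths not ascertained under the present wording may be hard to recover later.
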